## 4 STUDY DESIGN

### 4.1 Overall design

UP0073 is a randomized, 2-part single-dose crossover Phase 1 study. The study will enroll approximately 42 healthy participants into open-label Part A and 30 healthy participants (15 of Japanese origin and 15 of Chinese origin) into double-blind Part B at a single study site. A study overview of UP0073 is provided in [Figure 1-1](#).

#### 4.1.1 Part A

Part A is an open-label, randomized, 2 in-series crossover substudies, each with a fixed sequence complete block design of 3 treatment periods in healthy male and female participants. Each substudy evaluates the UCB0599 relative bioavailability of the new formulations (180mg film-coated tablet containing CCI with or without encapsulation) versus the current clinical

formulation (2x90mg granules in capsule) under both normal and elevated gastric pH conditions, respectively. See Section 3 for more details on the objectives and endpoints of the study.

Part A consists of the following (for a total duration of up to 68 days):

- A 28-day Screening Period (2 to 28 days before administration of study medication)
- A Baseline health status on admission to study site on Day -1.
- 6 treatment periods (each treatment period is followed by a 4-day Washout Period)
  - The first 3 periods include the evaluation of UCB0599 PK following its single-dose administration (180 mg) of each formulation under normal gastric pH conditions.
  - The second 3 periods include the evaluation of UCB0599 PK following its single-dose administration (180mg) of each formulation under the condition of elevated gastric pH. The elevated gastric pH will be achieved by co-administering esomeprazole 40mg QD over the duration of the 3 treatment periods (Day 14 to Day 33; see [Table 1-1](#)).
- A 7-day Safety Follow-Up (SFU) Period

In Treatment Period 1 through Period 3 for Part A, study participants will fast overnight for at least 10 hours prior to study medication administration on Day 1, Day 6, and Day 11, according to the randomization scheme (see [Table 1-1](#)), and will continue to fast for at least 4 hours post-study medication administration; thereafter participants will be given a standard breakfast or light snack. In Treatment Period 4 through Period 6, study participants will fast overnight for at least 9 hours prior to esomeprazole administration on Day 19, Day 24, and Day 29, and will continue to fast prior to study medication administration (1 hour following esomeprazole administration) and for at least 4 hours post-study medication administration (see [Table 1-1](#)); thereafter participants will be given a standard meal (ie, lunch). In between each Treatment Period, participants will undergo a 4-day Washout Period. On other days during the Treatment Period, study participants will receive standard meals and snacks at appropriate times as indicated by the clinic center (see [Table 1-3](#)). During the whole treatment, participants will remain under close medical supervision in the clinic.

On Day 33, after all the scheduled procedures have been performed, the participant may leave the clinic provided that, in the opinion of the Investigator, there are no safety concerns. Study participants will return to the clinic to complete the SFU assessments. Blood samples for determination of plasma UCB0599 and its [CC1](#) metabolites will be collected over 96 hours postdose (see Schedule of Activities, Section 1.3). Of note, for substudy 2 (Treatment Periods 4 through 6), the blood sampling time points will be based upon the timing of UCB0599 administration (to occur 1 hour after PPI administration).

#### **4.1.2 Part B**

Part B of this study is an ethnobridging study evaluating the safety, tolerability, and PK of a single oral dose of UCB0599 at 3 dose levels (90mg, 180mg, and 360mg) under normal gastric pH conditions in healthy participants of Japanese and Chinese origins. Each group of ethnic origin (N=15 total for each) will be randomized to a 4-treatment, 6-sequence, 2-period crossover study using UCB0599:placebo in a 4:1 ratio, as shown below and in the Study Schema ([Figure 1-1](#)). Sequence 6 will only commence after Sequence 5 has been completed for all 4 participants. Sequences 3 and 4 (Cohort 3) will only commence after Sequences 1 and 2 (Cohort 2) have been

completed for all 5 participants; Sequences 5 and 6 (Cohort 4) will only commence after Sequences 3 and 4 have been completed for all 5 participants allowing the SMC review to be carried out before the start of Sequence 5.

- Sequence 1: placebo 90mg, followed by placebo 180mg (N=1)
- Sequence 2: UCB0599 90mg followed by UCB0599 180mg (N=4)
- Sequence 3: placebo 180mg, followed by placebo 360mg (N=1)
- Sequence 4: UCB0599 180mg, followed by UCB0599 360mg (N=4)
- Sequence 5: placebo 360mg, followed by placebo 90mg (N=1)
- Sequence 6: UCB0599 360mg, followed by UCB0599 90mg (N=4)

See Section 3 for more details on the objectives and endpoints of the study.

No participant will ever receive both UCB0599 and placebo, and therefore no intra-participant comparison will be possible; the crossover aspect of the Part B design refers to the dose level over 2 periods in order to limit the number of participants to be recruited into this study. This design will allow the collection of UCB0599 data at each dose level for 8 study participants of each ethnic origin and the collection of dose-matching placebo data for 2 study participants of each ethnic origin for each dose. Participants will be blinded to the treatment (ie, UCB0599 or placebo), but not to the dosage within a sequence.

Part B consists of the following periods (for a total duration of up to 45 days):

- A 28-day Screening Period (2 to 28 days before administration of study medication)
- 2 treatment periods (for a total duration of up to 10 days)
  - Eligible study participants will commence the Treatment Period on Day -1. Each participant enrolled will receive a single oral dose of UCB0599 (formulation selected in Part A) or placebo on Day 1 (90mg or 180mg or 360mg of UCB0599 or matching placebo), in accordance with the randomization schedule (see [Table 1-2](#)). Study participants will be administered the second single oral dose of UCB0599 or placebo on Day 6. In between each Treatment Period, participants will undergo a 4-day Washout Period. During the whole treatment, participants will remain under close medical supervision in the clinic.
- A SFU Period (7 days after the last study medication administration)

In Treatment Period 1 through Period 2 for Part B, study participants will fast overnight for at least 10 hours prior to study medication administration on Day 1 and Day 6, and continue to fast for at least 4 hours post-study medication administration. Thereafter participants will be given a standard breakfast or light snack (see [Table 1-2](#) and [Table 1-4](#)).

On Day 10, after all the scheduled procedures have been performed, the study participant may leave the clinic provided that, in the opinion of the Investigator, there are no safety concerns. Study participants will return to the clinic to complete the SFU assessments. Blood samples for determination of plasma UCB0599 and its [CC1](#) metabolites will be collected over 96 hours postdose (see Schedule of Activities, Section 1.3). Up to a maximum of 6 replacements will be targeted in case participants discontinue Part B (see Section 7).

There is 1 planned interim analysis for Part B in which safety data from Part B will be analyzed (Section 9.8). Throughout the study, data will be reviewed on an ongoing basis by an SMC.

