## **6.3 Measures to minimize bias: randomization and blinding**

Part A is an open-label, randomized, 2 in-series crossover substudies, each with a fixed sequence complete block design of 3 treatment periods in healthy male and female participants. This portion of the study is planned to enroll up to 42 study participants, in which 7 participants will

be randomized (approximately 6 completers) to each sequence. Randomization numbers will be assigned at the site in an unblinded fashion and will be entered into the eCRF.

In Part B, 15 study participants of each ethnic origin will be randomized to the 4 treatments following a UCB0599:placebo 4:1 ratio (see Section 4.1 for study design details). Participants will be blinded to the treatment (ie, UCB0599 or placebo), but not to the dosage within a sequence. As study participants are being screened for Part B, participants will be randomized to blocks of 2 sequences at a time: Sequences 1 and 2 (Cohort 2), followed by Sequences 3 and 4 (Cohort 3), and finally Sequences 5 and 6 (Cohort 4) after the SMC review.

An interactive response technology (IRT) will be used for assigning eligible participants (in Part A and Part B) to a treatment regimen (as applicable) based on a predetermined production randomization and/or packaging schedule provided by UCB (or designee). The randomization schedule will be produced by the IRT vendor. The IRT will generate individual assignments for kits of the study medication, as appropriate, according to the visit schedule.

To enroll a study participant (Visit 1), the Investigator or designee will contact the IRT and provide brief details about the participant to be enrolled. Each participant will receive a 5-digit number assigned at screening that serves as the participant identifier throughout the study. The participant number will be required in all communication between the Investigator or designee and the IRT regarding a particular participant. Participant numbers and kit numbers will be tracked via the IRT.

To randomize a participant, the Investigator or designee will contact the IRT and provide brief details about the participant to be randomized. The IRT will automatically inform the investigator or designee of the participant's randomization number. The IRT will allocate kit numbers to the participant based on the participant number during the course of the study. The randomization number must be incorporated into the eCRF.

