All participant treatment details will be allocated and maintained by the IRT. The following individuals will have received the randomization code at the start of the UP0073 study:

- Designated CRO bioanalytical staff analyzing samples
- Sponsor clinical study supply staff
- IRT provider

The following individuals may have access to the randomization code as indicated:

- Sponsor patient safety staff as needed for reporting SAEs to regulatory authorities

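### Protocol 4.1.2 makes Sequence 6 wait for four Sequence 5 completers that the design never has, and the order it implies conflicts with concurrent, blinded dosing of Cohort 4

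*Protocol*

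**What the plan says.** Part B has three cohorts per ethnic group, each pairing a placebo sequence with an active one. Protocol Section 4.1.2 sets the staging and includes this rule: "Sequence 6 will only commence after Sequence 5 has been completed for all 4 participants". The list a few lines below it gives the two sequences concerned, per ethnic group, as "Sequence 5: placebo 360mg, followed by placebo 90mg (N=1") and "Sequence 6: UCB0599 360mg, followed by UCB0599 90mg (N=4").

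The sentences that follow the rule in Section 4.1.2 give Sequences 5 and 6 the same start condition: both wait until Sequences 3 and 4 are complete for all five participants, so that the Safety Monitoring Committee (SMC) can review first. The synopsis and SAP Section 1.2.2 carry this cohort rule without the extra sentence.

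Section 6.3 governs allocation. It says that "participants will be randomized to blocks of 2 sequences at a time", with the last pair described as "and finally Sequences 5 and 6 (Cohort 4) after the SMC review". It adds that "The randomization schedule will be produced by the IRT vendor". The Part B schedule of activities (Table 1-4) places randomisation on Day -1. Participants know their dose but not whether it is active or placebo.

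**The concern.** The sentence raises two problems.

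- **Count.** It calls for four Sequence 5 participants, and the list below it has one per ethnic group. Taken literally, Sequence 6 could never start.
- **Order.** If the number is treated as a slip and the order is kept, an all-placebo sequence must finish before an all-active one begins. Entry order in Cohort 4 would then reveal treatment to anyone who has read Section 4.1.2, without access to the randomisation code.

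The stake is the blind for safety judgements in the last cohort. The investigator assesses causality for every adverse event (Appendix 3) and sits on the SMC (Section 10.1.6). The investigator is not on the list introduced by "The following individuals will have received the randomization code at the start of the UP0073 study". One serious event that the investigator judges related is a halting criterion (Section 7.1.5), and SAP Section 5.5.2 tabulates treatment-emergent events by relationship to study medication. These judgements should be made without knowing the treatment.

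**Working it through.** **Inputs.** Sequence sizes per ethnic group from the list in Protocol 4.1.2: Sequences 1 to 6 = 1, 4, 1, 4, 1, 4, where odd numbers are placebo and even numbers active. All counts are planned numbers without replacements.

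**Step 1: reproduce the plan's own counts.**

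- Per ethnic group: 1 + 4 + 1 + 4 + 1 + 4 = 15. Over both groups: 2 × 15 = 30. Both agree with the plan.
- Per cohort: 1 + 4 = 5, a 4:1 ratio. Agrees.
- 90 mg: active 4 (Sequence 2) + 4 (Sequence 6) = 8; placebo 1 (Sequence 1) + 1 (Sequence 5) = 2.
- 180 mg: active 4 (Sequence 2) + 4 (Sequence 4) = 8; placebo 1 (Sequence 1) + 1 (Sequence 3) = 2.
- 360 mg: active 4 (Sequence 4) + 4 (Sequence 6) = 8; placebo 1 (Sequence 3) + 1 (Sequence 5) = 2.

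The stated 8 active and 2 placebo per dose are reproduced at every dose. The five participants named in the neighbouring staging sentences also match the per-group cohort size.

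**Step 2: test the figure of four.**

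- Sequence 5 per ethnic group = 1; over both groups = 2 × 1 = 2. SAP Table 5-4 confirms one Chinese and one Japanese participant. Neither count is 4. Four is the size of Sequence 6.
- If Sequence 5 really had 4 per group, the group total would be 15 − 1 + 4 = 18. Cohort 4 would be 4 + 4 = 8 at 1:1, and placebo at 90 mg and at 360 mg would each be 1 + 4 = 5. The plan has 15, 5 at 4:1, and 2.
- Replacements (at most six in Part B) do not rescue the figure. A replacement stands in for someone who withdrew, so the planned number of Sequence 5 completers stays at 1 per group.

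**Step 3: test the order.**

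| Place | Rule for Sequences 5 and 6 |
|---|---|
| 4.1.2, disputed sentence | Sequence 5 completed, then Sequence 6 starts |
| 4.1.2, following sentences | Both wait for Sequences 3 and 4 |
| Synopsis | Both wait for Sequences 3 and 4 |
| 6.3 | Randomised together as Cohort 4 after SMC review |
| SAP 1.2.2 | Both wait for Sequences 3 and 4; SMC review before both |

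The synopsis, SAP 1.2.2 and the following sentences of 4.1.2 set only an earliest start, so they neither contain the 5-then-6 rule nor strictly contradict it. The conflict is with Section 6.3, because concurrent randomised dosing within the pair and completing one member before the other starts cannot both happen.

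**Step 4: size the conditional worst case** (figure ignored, order kept, schedule built on it).

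- Participants in Cohort 4: 2 × (1 + 4) = 10 of 30 (33%).
- Active: 2 × 4 = 8 of 2 × (4 + 4 + 4) = 24. Placebo: 2 × 1 = 2 of 2 × (1 + 1 + 1) = 6.
- Chance that the first Cohort 4 entrant in a group is on placebo: 1/5 = 20% in a randomly ordered block of five, against 100% under the sentence. The 20% assumes one block of five per ethnic group, which the documents do not spell out.

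If the schedule follows Section 6.3, the number affected is 0.

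**The case against.** The strongest reply is that this is an editorial slip with no demonstrated effect. The rule contradicts the list printed just below it, so it cannot be carried out as written and would prompt a query. It appears nowhere else, and the section that governs randomisation is clear. For harm to follow, whoever built the schedule would have to drop the impossible number silently, keep the order and disregard Section 6.3. All of that stands, and it is why the point is minor.

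A reader might also infer that the order rule is logically incompatible with block randomisation. That goes too far: a list could be generated as a block and dosing then staggered. Randomisation on Day -1 makes this awkward but does not rule it out. The conflict is with concurrent, blinded dosing of the pair.

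The impact is limited even in the worst case. The co-primary PK endpoints are assay-based, and the bioanalytical staff hold the code by design. The primary safety endpoints count events without reference to relatedness. Section 7.1.5 provides for a case review to confirm causality before dosing is halted.

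One reply does not stand: that the order might be deliberate caution. An all-placebo lead-in gives no safety information about the active drug, and the documents offer no rationale for it.

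**Conclusion.** The sentence is wrong as written. Its condition needs four Sequence 5 participants, and the design has 1 per ethnic group (2 overall). Read with the order kept, it conflicts with concurrent, blinded randomised dosing of Sequences 5 and 6 under Section 6.3. It is current, operative text on allocation order in a double-blind part, so it deserves correction, but it is a minor internal inconsistency.

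The effect is conditional. At worst, treatment for 10 of 30 Part B participants (8 active, 2 placebo) could be inferred from entry order. If the IRT follows Section 6.3, nobody is affected. The worst case assumes planned numbers and a schedule built on this sentence. It holds whether the order is applied within each ethnic group or across both, a detail that the sentence leaves open.

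A reader might infer that Cohort 4 was in fact unblinded, or that the Part B PK results are open to bias. The documents support neither: they do not include the IRT specification, and the PK endpoints and sample sizes do not depend on the sentence.

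**What to change.** Delete the sentence from Protocol 4.1.2, so that the section agrees with the synopsis, Section 6.3 and SAP 1.2.2. Confirm that the IRT specification randomises Sequences 5 and 6 as one blinded block of 1 placebo and 4 active per ethnic group.

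The cost is one deleted sentence and one check. No participants, visits or SMC meetings are added, and no sample-size or PK analysis figure changes.

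Two separate editorial notes could be handled in the same amendment, although they add no weight here. Section 9.8 describes the review after Cohort 3 as a step to the next dose level, although active 360 mg is already given in Sequence 4, Period 2. The end of Section 4.1.2 describes the single planned interim analysis as a Part B safety analysis, while Section 9.8 and SAP 5.7 define it as a PK analysis after Part A.

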## 4.2 Scientific rationale for study design

UP0073 has a 2-part design and is intended to evaluate the relative bioavailability of 2 new UCB0599 formulations (180mg film-coated tablet containing **CCI** with or without encapsulation) versus the current clinical formulation (ie, 2x90mg granules in capsule); to evaluate the effect of esomeprazole on the PK of UCB0599 in healthy participants (Part A, open-label); and to assess the safety, tolerability, and PK of UCB0599 in healthy participants of Japanese and Chinese origins (Part B, double-blind).

Previously published studies and nonclinical research demonstrate that significant ethnic differences can exist in the metabolism of some drugs, which are caused by cytochrome P450 (CYP) polymorphism. Cytochrome 2D6, 2C19, and 2C9 polymorphisms account for the most frequent variations in the Phase 1 metabolism of drugs. For example, approximately 5 to 14% of Caucasians and 0 to 1% of Asians lack CYP2D6 activity and are known as poor metabolizers. However, there is insufficient evidence to show that there are some ethnic differences for CYP3A4 polymorphism. Based on preclinical drug metabolism studies, no differences in exposure are expected in healthy participants of Japanese and Chinese origins compared with Caucasian participants.

Part B of this study will be conducted to generate continued clinical development of UCB0599 doses up to 360mg/day. The rationale for testing the proposed dose levels of UCB0599 (90mg, 180mg, and 360mg/day single dose) in this healthy population is based on data from previously conducted studies (UP0030, UP0077, and UP0078) as well as PK information for multiple dose exposures of 180mg/day for up to 21 days in elderly healthy volunteers (defined as  $\geq 55$  and  $\leq 75$  years of age) (see Section 4.3 for more details). The PK analysis of UCB0599 revealed that exposure increased close to proportionally with increased doses between 45mg and 450mg (single doses tested). Furthermore, multiple dose exposures ( $AUC_{\text{tau}}$ ) were predictable from single dose exposures, indicating linear PK behavior. Therefore, the evaluation of UCB0599 180mg single dose to assess relative bioavailability should provide adequate guidance for the development of a new formulation for further clinical development in Phase 2 and 3 studies.

Approximately 25% of PD patients receive acid reducing agents as concomitant medications to manage acid reflux through the elevation of the gastric pH (Lai et al, 2020). UCB0599 is a weak basic drug ( $pK_a$  of 6.8) following oral dose administration in humans, and is expected to undergo pH-dependent absorption over different segments of the GI tract, with more absorption in the intestine (pH range 6 to 8) compared with the upper segments of the GI tract (pH range is 2 to 6). However, it is not known whether an elevated gastric pH affects the systemic exposure of UCB0599 and its metabolites (**CCI** metabolite) for the current clinical formulation. For this reason, in Part A, UP0073 will evaluate 2 formulations (ie, film-coated tablet containing **CCI** with or without encapsulation) to assess the relative bioavailability of 180mg UCB0599 compared with the current clinical formulation (ie, granules in capsule) in healthy participants. The addition of **CCI** excipient to the new tablet is expected to create a “microenvironment” in the tablet which should allow UCB0599 to dissolve uniformly in the stomach independent of gastric pH (Badawy and Hussain, 2007).

The use and inclusion of **CCI** is supported by results from biorelevant dissolution testing (Taniguchi et al, 2014). Data indicate that the encapsulation of the tablet may result in an improved robustness in vitro in some biopredictive in-vitro experiments. This in vitro observation may be explained by the fact that the presence of the capsule results in an intimate contact between the active pharmaceutical ingredient (API) and acidifier **CCI**, thereby resulting in higher concentrations of **CCI** close to the surface of the API (Badawy and Hussain, 2007).

As the current study will evaluate healthy participants, elevation of the gastric pH will be achieved through the administration of a PPI (esomeprazole), in which drug systemic exposure will be compared in the absence or presence of PPI. Thus, this approach will also allow comparison of UCB0599 systemic exposure from film-coated tablets with or without encapsulation to inform formulation development. The current complete block study design in Part A will evaluate each study participant under both elevated and normal gastric pH conditions.

#### **4.2.1 Patient input into design**

Not applicable.

#### **4.3 Justification for dose**

In Part A, the UCB0599 dose level of 180mg single dose is being selected based on the PK properties of UCB0599. Upon oral intake of doses 90mg to 450mg, both  $C_{max}$  and AUC increase approximately linearly with dose, indicating dose proportionality. In addition, clinical data show that AUC at steady state over the dose interval is similar to  $AUC_{inf}$  after single dose, suggesting linear behavior of UCB0599 in the clinically tested dose range of 180mg/day to 360mg/day; hence UCB0599 180mg single dose administration is projected to provide exposure information that can be used to bridge between the current clinical formulation and a new formulation.

In Part B, UP0073 will be conducted to generate supportive safety, tolerability, and PK data in healthy participants of Japanese and Chinese origins for the continued clinical development of UCB0599 doses up to 360mg/day. The rationale for testing the proposed dose levels of UCB0599 (90mg, 180mg, and 360mg/day single dose) in this healthy population is based on data from previously conducted studies (UP0030, UP0077, and UP0078). UP0030 tested 90mg twice per day for 21 days in elderly healthy participants to assess the safety, tolerability, and PK information for multiple dose exposures. This study showed that UCB0599 exposures increased linearly (both  $C_{max}$  and AUC) across the tested dose range (90mg to 450mg, single dose). UP0077 provided the safety, tolerability, and PK of UCB0599 for multiple doses of 180mg/day and 360mg/day in PD patients. The collective data from UP0030 and UP0077 further showed that exposure after multiple dosing is predictable from single-dose data and that dose-exposure relationship is similar between (elderly) healthy participants and PD patients. These 2 dose levels (180mg/day and 360mg/day, achieved by twice daily dosing) were selected for the proof-of-concept study PD0053 to obtain initial evidence of UCB0599 efficacy in slowing PD disease progression. The therapeutic dose of UCB0599 is likely to be  $\leq$ 360mg/day. Hence, 360mg was chosen as the maximum single dose in Part B of this study; 2 dose levels below 360mg have been selected (90mg and 180mg) and are set in a common ratio of 2 to adequately evaluate the PK characteristics and dose proportionality of UCB0599. Therefore, these 3 dose levels (90mg, 180mg, and 360mg) are believed to be appropriate doses for this portion of the study, and steady state PK will be projected based on single dose data.

Further information regarding UP0030, UP0077, and UP0078 is provided in the most recent IB.

